Affected Section(s)	Summary of Revisions Made	Rationale
Title page	Updated to add GCP and Confidentiality statements	Consistency with other protocol
Protocol Amendment History	Add a list of changes since Version 3.0	Correctness
Signature page	Revised to include all functional areas	Correctness
Section 2	Revised grammar, punctuation, spelling; added safety endpoints, revised study schema and Schedule of Assessments	Correctness
Section 3	Updated abbreviations	Correctness
Section 4	Updated editorial items (grammar, punctuation, spelling)	Correctness
Section 5	Separated Objectives and Endpoints, which had been in the same section	Correctness
Section 6	Editorial corrections; updated the definition of End of Study	Correctness
Section 8	Moved all information related to treatment of subjects to Section 8 from Section 9	Correctness
Section 9	Added a section that describes all assessments	Completeness
Section 10	Corrected missing elements from study procedures	Completeness
Section 11	Corrected language in the description of withdrawal of a subject	Correctness
Section 12	Editorial corrections	Completeness
Section 13.1.3	Added missing information	Completeness
Section 14	Added references	Completeness
Appendices	Updated with references (sources), and corrected procedures	Completeness

Summary of Changes from Version 2.0 to 3.0

Affected Section(s)	Summary of Revisions Made	Rationale
Throughout the protocol	Administrative clarifications located throughout the protocol	To correct pagination and version number inconsistencies
Schedule of Assessments	Added Adverse Event Assessment to screening visit	To add consistency throughout protocol
Schedule of Assessments / 9.3.1.	Added the use of Polar Beat H10 heart rate sensor to both CRC exercise sessions.	Site will be using this to monitor subject heart rate during exercise sessions.
Table 3	Removed exploratory endpoint: “Proportion of time with 80% max heart rate during exercise sessions.”	This endpoint is no longer applicable as 80% is a target heart rate, but not required, during exercise sessions.
8.1	Inclusion criteria #4: Updated inclusion criteria to include pmol/L equivalent of ng/mL for random C-peptide.	The local lab will report this value using pmol/L.
11.4.4	Revised wording for start time of collection of adverse events from starting “at Visit 2” to “from time of consent”	To add consistency throughout protocol.

2. PROTOCOL SUMMARY

2.1. Synopsis

Title	A Phase 2 Randomized, Placebo-Controlled, Double-Blind, Parallel Study To Evaluate Glucagon RTU (Glucagon Injection) Compared To Standard Of Care For The Prevention Of Exercise-Induced Hypoglycemia During Regular Aerobic Exercise In Adults With Type 1 Diabetes.
Study Description	
This study is a randomized, placebo-controlled, double-blind, two-treatment, two-period, crossover comparison in a clinical research center (CRC) setting followed by a randomized, placebo-controlled, double-blind, 2-arm parallel comparison with a third open-label arm in the Outpatient Phase. The purpose of the study is to evaluate the preliminary efficacy of Glucagon Ready-to-Use (RTU) to prevent exercise-induced hypoglycemia in adults with Type 1 diabetes mellitus (T1D) who perform regular, moderate-to-high intensity, aerobic exercise of at least 45 minutes duration in an inpatient setting and at least 30 minutes duration in the outpatient setting, and who receive daily insulin treatment via a subcutaneous infusion pump and to monitor safety in this population.
 
During the CRC Phase, each subject will undergo two, 45-minute morning aerobic exercise sessions. Subjects will be randomized to receive the first treatment at Visit 3 and crossed over to the second treatment at Visit 4. All CRC exercise sessions will take place in the morning, following an overnight fast. At 5 minutes prior to each exercise session, subjects will reduce their basal rate of insulin infusion by 50% and maintain this reduction for the duration of exercise. Immediately after making the basal rate insulin reduction, subjects will self-administer one of the following randomly assigned interventions:
 
 1. Placebo (vehicle) 2. Glucagon RTU 
During the 12-week Outpatient Phase, subjects will be assigned randomly in a 1:1:1 ratio to 1 of the following interventions to self-administer prior to moderate-to-high intensity aerobic exercise sessions lasting at least 30 minutes:
 
 1. A 50% reduction in basal rate insulin 5 minutes before exercise + pre-exercise injection of placebo (blinded) 2. A 50% reduction in basal rate insulin 5 minutes before exercise + pre-exercise injection of Glucagon RTU (blinded) 3. No reduction in basal rate insulin + pre-exercise injection of Glucagon RTU (open-label)
Objectives	
Primary Objective:
 
To evaluate if the subcutaneous (SC) administration of Glucagon RTU (Glucagon Injection) just before exercise, with or without a 50% reduction in basal rate insulin, compared to a 50% basal rate insulin reduction alone, prevents the occurrence of hypoglycemia (ie, blood glucose \leq70 mg/dL; 3.89 mmol/L) measured by blood glucose meter (BGM) during and after

	moderate-to-high intensity aerobic exercise by adult subjects with T1D in an outpatient setting.
	
Secondary Objectives:
 
 1. To evaluate how Glucagon RTU (Glucagon Injection) contributes to prevention of hypoglycemia during exercise and post-exercise recovery. 2. To evaluate the effect of Glucagon RTU (Glucagon Injection) on insulin utilization during 12 weeks of out-patient exercise. 3. To evaluate the effect of Glucagon RTU (Glucagon Injection) on patient-reported outcomes (PROs) of: Barriers to Physical Activity Diabetes (Type 1) (BAPAD-1), Hypoglycemia Fear Survey (HFS) and Hypoglycemia Confidence Scale (HCS) after 12 weeks of outpatient exercise.
Endpoints	
Primary Endpoint: Incidence of hypoglycemia (ie, blood glucose \leq70 mg/dL; 3.89 mmol/L) associated with an exercise session across 12 weeks of outpatient treatment as measured by blood glucose measurements (BGM).
 
Key Secondary Endpoints:
 
 1. Glucose levels below target range, measured by unblinded CGM (inpatient and outpatient), defined as both time (in minutes) and mean decremental area over the curve (AUC(0-300 min) in minutes*mg/dL) during exercise: 
 • Below range, as defined by interstitial glucose (IG) \leq 70 mg/dL (3.89 mmol/L) • Below range, as defined by IG between 54 to - 70 mg/dL (3 – 3.89 mmol/L) • Below range, as defined by IG $<$ 54 mg/dL (3 mmol/L) • Proportional time (percentage time within hypoglycemia IG \leq 70 mg/dL (3.89 mmol/L) and clinically significant hypoglycemia IG $<$ 54 mg/dL (3 mmol/L)) 2. Change from Baseline at the end of the Outpatient Phase in the following PROs: Barriers to Physical Activity in Diabetes (Type 1) (BAPAD-1), Hypoglycemia Fear Survey (HFS-II), Hypoglycemic Confidence Scale (HCS). 
Other Secondary Endpoints
 
 • Change from Baseline at Weeks 4, 8, and 12 in insulin utilization as reported by the subject in the Outpatient Phase.
Safety Endpoints	Safety endpoints include the following: summaries of number of subjects (%) with adverse events, including serious adverse events; change from Baseline in vital signs and clinical laboratory test values; number of

[figure not shown]
Glucagon RTU (Glucagon Injection)
Protocol XSMP-204

Version 4.0

	abnormal and clinically significant 12-lead ECG results. All safety parameter results will be listed.
Study Population	The study will include 48 male and female subjects in North America with Type 1 diabetes (T1D) aged 18 to 65 years at Screening, who engage in regular, moderate-to-high-intensity aerobic exercise at least 30 minutes in duration, and who receive daily insulin therapy via SC infusion pump. Approximately 100 subjects may be screened to obtain 48 randomized subjects.
Phase	2
Description of Sites/Facilities Enrolling	LMC Manna Research [name]
Principal Investigator	[name], FRCPC, FACE
Description of Study Intervention	Glucagon RTU is a non-aqueous, injectable liquid formulation of glucagon. Glucagon RTU consists of synthetic glucagon peptide dissolved in a DMSO diluent, with trehalose and mannitol added as stabilizing excipients. Glucagon RTU is presented in a 2-mL glass vial (1 mL fill). The placebo consists of the matching Glucagon RTU vehicle without glucagon in the same vial presentation. Both products will be administered SC around the umbilicus using a staked-needle syringe. The dose is 30 μ L per injection, which delivers 150 μ g of glucagon for the active formulation.
Study Duration	The estimated duration of the entire study is 8 months.
Participant Duration	Participant study duration is approximately 20 weeks (5 months). Subjects will participate in a 4-week Screening Period, a 2-week CRC Phase, 12-week Outpatient Phase, and a 2-week for the End of Study Visit.

2.2. Schema

Figure 1: Schema of Study Design

1 Single dose cross-over treatment in a CRC setting will be separated by 2 to 28 days.

2 Outpatient setting where patients are randomized to 1 of 3 parallel treatment arms.

3 Randomization into 1 of 3 Treatment Arms at the beginning of the study:

Treatment A: Pump reduction of 50% in basal rate 5 minutes before exercise for the duration of exercise, plus pre-exercise placebo injection (30 µL vehicle)

Treatment B: Pump reduction of 50% in basal rate 5 minutes before exercise for the duration of exercise, plus pre-exercise Glucagon RTU injection (30 µL active - 0.15 mg)

Treatment C: No pump reduction for the duration of exercise, plus pre-exercise Glucagon RTU injection (30 µL active - 0.15 mg)

2.3. Schedule of Activities

Table 1 Schedule of Assessments and Procedures

Assessment	Visit 1	Visit 2	Visit 3 ^o CRC 1	Visit 4 ^o CRC 2	Visits 5 to 10 Outpatient Phase	Visit 11 Follow-up ^f /ET
	Screening Day -28 to -3	CGM Placement Day -2 to -1	Treatment Period 1 (Days 1 ^{a,b,c})	Treatment Period 2 Day 3 to 29 ^d	Treatment Period 3 Day 4 to 113 ^e	
Informed consent	X					
Medical History/ Demographics	X					
Inclusion/exclusion criteria	X					
Concomitant medications (including insulin pump data)	X	X	X	X	X	X
Height, weight and physical examination	X					X
12-lead ECG	X					X
Vital signs	X		X	X	X	X
Urine pregnancy test	X		X	X	X	X
Urine drug screen	X					
Hematology	X					X
Clinical chemistry	X					X
HbA1c	X					X
Plasma Glucose	X					X
C-peptide	X					X
Immunogenicity ^g			X		X	X
CGM		X ^d	X ^h	X ^h	X ^h	X ^h
Exercise ^{i,o}			X	X		
BGM ^k			X	X ^j	X ^j	X ^j
Study drug administration			X	X ^l	X	
Wearable Activity Monitors (Fitbit Ionic and Polar Beat H10)			X ^m	X ^m	X ⁿ	X ⁿ
HBV, HCV, HIV Screen	X					

Glucagon RTU (Glucagon Injection)
Protocol XSMP-204

Version 4.0

Assessment	Visit 1	Visit 2	Visit 3 ^a CRC 1	Visit 4 ^a CRC 2	Visits 5 to 10 Outpatient Phase	Visit 11 Follow-up ^f /ET
	Screening Day -28 to -3	CGM Placement Day -2 to -1	Treatment Period 1 (Days 1 ^{a,b,c})	Treatment Period 2 Day 3 to 29 ^d	Treatment Period 3 Day 4 to 113 ^e	
Outpatient Study Training				X		
Diary ⁱ			X	X	X	X
Glucose Tabs Log			X	X	X	X
Randomization			X			
8-Hour fast	X		X	X		X
Venous blood glucose (YSI)			X	X		
BAPAD-1 Questionnaire			X			X
Draize Scale			X	X		
HFS			X			X
Hypoglycemia Confidence Scale			X			X
Injection Site Discomfort Description and Duration Questionnaire			X	X		
Adverse event review	X	X	X	X	X	X

*Visits will occur every 2 weeks during the out-patient phase. The visit window is +/- 3 days for the outpatient visits.
 BAPAD-1 = Barriers to Physical Activity in Type 1 Diabetes Scale; BGM = blood glucose monitor; CRC = Clinical Research Center; CGM = continuous glucose monitor; ECG = electrocardiogram; HBV = hepatitis B virus; HCV = hepatitis C virus; HFS = Hypoglycemia Fear Survey; HIV = human immunodeficiency virus; YSI = Yellow Springs Instrument

- a. As long as the subject has 2 days of rest between each CRC visit.
- b. Subjects will be instructed not to exercise between Visit 2 and Visit 3.
- c. Questionnaires to be completed are Barriers to Physical Activity Diabetes (Type 1) (BAPAD-1), Hypoglycemia Fear Survey (HFS) and Hypoglycemia Confidence Scale (HCS).
- d. CGM will be placed approximately 24-48 hours prior to data collection at CRC Visit 2.
- e. Collection timepoints \pm 2 minutes are: -15 minutes, 0 minutes (just before initiation of exercise), and at 15, 30, 45, 60 and 75 minutes after initiation of exercise.
- f. Follow-Up occurs 14 days after the last exercise period.
- g. An immunogenicity sample will be drawn before the first dose of investigational product, every four weeks (28 days \pm 2 days) and at the End of Study visit.
- h. CGM data will be downloaded.
- i. During the CRC Phase of the study, subjects will perform moderate-to-high-intensity exercise of at least 45 minutes duration, with each exercise session separated by at least 2 days during the inpatient phase of the study. During the Outpatient Phase of the study, subjects will be asked to maintain a weekly exercise average of 2 to 3 sessions weekly of at least 30 minutes. Exercise data will be downloaded from the wearable device. Data include heart rate, calories burned, daily steps, floors climbed, distance covered, active minutes.
- j. BGM Measurements will be performed at the following timepoints during CRC visits, \pm 2 minutes:
 - -15 minutes (both YSI and BGM)
 - Time 0 (immediately before exercise) (both YSI & BGM))
 - 15 minutes (YSI only)
 - 30 minutes (both YSI & BGM)
 - 45 minutes (both YSI & BGM, end of exercise)

Glucagon RTU (Glucagon Injection)
Protocol XSMP-204

Version 4.0

- 60 minutes (YSI only)
- 75 minutes (both YSI & BGM, thirty minutes after completion of exercise)

k. BGM data will be downloaded at each patient visit.

l. Investigational Product (IP) for first outpatient visit will be dispensed at the end of visit 4.

m. Subject will wear both Fitbit Ionic and Polar Beat H10 heart rate sensor during this visit.

n. Subject will wear only the Fitbit Ionic during these visits.

o. Prior to beginning the exercise session, if the subject's blood glucose is below 100 mg/dL the subject is allowed to take dextrose tabs (e.g., 2-4 tabs) to raise the blood glucose, and the blood glucose verified to be within 100-180 mg/dL (5.56 – 10 mmol/L). The number of dextrose tabs and time administered are recorded.

Prior to beginning the exercise session, if the blood glucose is >180 mg/dL after repeat test, then the investigator may treat with an intravenous (IV) bolus dose of regular insulin, per discretion, to bring the subject into the required blood glucose range. Before initiating study treatment, at least 40 minutes should have passed from the last dose of administered insulin and the subject's glucose level should be within the range of 100 to 180 mg/dL. At discretion, the investigator may reschedule the visit to occur after a minimum wait of 24 hours. The visit should be re-scheduled so it occurs within the originally defined visit window. For example, a rescheduled Visit 3 (CRC 1) should occur within 28 days of Visit 1 (Screening), while a rescheduled Visit 4 (CRC 2) should occur within 28 days of a completed Visit 3 (CRC 1)..

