12.2. Sample Size Determination

The primary endpoint of the study is the incidence of hypoglycemia (glucose \leq 70 mg/dL (3.89 mmol/L)) associated with an exercise session, which occurred within the 12 weeks outpatient follow-up, as measured by BGM. The null hypothesis is that there is no difference between the treatment groups in the mean incidence of exercise associated hypoglycemia, and the alternative is there is a difference between the treatment groups in terms of the mean incidence of exercise associated hypoglycemia. With an effect size estimate of 0.262 (variance of means 59, common standard deviation 15), 80% power and an alpha of 0.05, using a one way analysis of variance, 14 subjects per treatment group in the Outpatient Stage is required.

Accounting for 15% attrition, a total of 48 subjects will be randomized.

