12.4.2. Analysis of the Primary Efficacy Endpoint(s)

The primary efficacy analysis will be analyzed by ANOVA comparing the mean incidence rate among the 3 treatment groups. All statistical significance testing will be 2-sided with a p-value <0.05 . Efficacy endpoints will be analyzed using the ITT and PP analysis populations. After performing the F-test and if an overall $p<0.05$ is achieved, post-hoc analysis of group means will be conducted to statistically determine which group means differ.

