### 1.3 DETERMINATION OF SAMPLE SIZE

The primary endpoint of the study is the incidence of hypoglycemia (glucose  $\leq$  70 mg/dL (3.89 mmol/L)) associated with an exercise session, which occurred within the 12-week outpatient follow-up, as measured by BGM. The null hypothesis is that there is no difference between the treatment groups in the incidence of exercise-associated hypoglycemia, and the alternative is there is a difference between the treatment groups in terms of the incidence of exercise-associated hypoglycemia. With an effect size estimate of 0.262 (variance of means 59, common standard deviation 15), 80% power and an alpha of 0.05, using a one-way analysis of variance, 14 subjects per treatment group in the Outpatient Stage is required. Accounting for 15% attrition, a total of 48 subjects will be randomized.

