## 4. STATISTICAL METHODOLOGY

### 4.1 Definition of Analysis Population

**All Screened Subjects:** All Screened subjects will include any subject who signed the informed consent form.

**Intention to Treat (ITT) Population:** All randomized subjects regardless of whether they received Study Drug.

**Per Protocol (PP) Population:** ITT participants who completed a qualified exercise session, and who was dosed within the study window and did not meet any of the key exclusion criteria at screening. The definition of qualified exercise is defined in Section 2.4.

**Safety Population:** All randomized subjects who received any amount of Study Drug.

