#### **4.3.6 Primary Endpoint Analysis:**

The primary efficacy hypothesis test for the study is as follows:

Null Hypothesis: There is no difference between the treatment groups in the mean incidence of hypoglycemia (glucose  $\leq 70$  mg/dL (3.89 mmol/L)) associated with an exercise session occurring within the 12 weeks of out-patient treatment as measured by BGM.

Alternative Hypothesis: There is a difference between treatment groups in the mean incidence of hypoglycemia (glucose  $\leq 70$  mg/dL (3.89 mmol/L)) associated with an exercise session occurring within the 12 weeks of out-patient treatment as measured by BGM.

Incidence rate per subject is calculated by summing the number of exercise sessions completed within 12 weeks and dividing this denominator by the number of hypoglycemic events that

occurred during those exercise sessions (Incidence Rate = number of exercise sessions / inter/post-exercise hypoglycemic events). Events associated with an exercise session are defined as hypoglycemic events that occur during or within 30 minutes of exercise completion.

The primary efficacy analysis will be analyzed by ANOVA comparing the mean incidence rate between the three treatment groups. All statistical significance testing will be two-sided with a p-value  $<0.05$ . Efficacy endpoints will be analyzed using the ITT and PP analysis populations for Outpatient phase, if performed F-test yields an overall p-value less than 0.05 ( $p<0.05$ ), post-hoc analysis of groups means will be conducted to statistically determine which group means differ.

Parameters that do not meet normality criterion will be analyzed non-parametrically. Overall treatment effect will be assessed using Friedman's test. If the overall treatment effect is significant in the Friedman's test, pairwise treatment comparisons will be assessed using the following tests.

- If the difference between two treatments is normally distributed (i.e., the p-value is  $\geq 0.05$  for Shapiro-Wilk test, the Tukey Test will be used.
- If the difference between two treatments is not normally distributed and the distribution is highly skewed, then the sign test/Kruskal Wallis test will be used.

Example of SAS syntax code that can be used for primary endpoint analysis is provided in APPENDIX 1.

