### **4.6 APPENDICES**

#### **4.6.1 APPENDIX 1. Example of SAS syntax code for primary endpoint analysis.**

The following SAS syntax code can be referred to during programming of primary endpoint analysis:

```
PROC ANOVA DATA = clover;
  CLASS trt_o;
  MODEL param = trt_o;
RUN;
```

Alternative:

```
PROC GLM DATA = xx;
  CLASS trt_o;
  MODEL param = trt_o/ ss3;
  LSMEANS trt_o / PDIFF CL ALPHA=0.05;
RUN;
```

Alternative:

```
PROC MIXED DATA=school METHOD=type3;
  CLASS trt_o;
  MODEL param= trt_o;
RUN;
```

The following SAS syntax example code can be referred to during testing the normality of the residuals using the Shapiro-Wilk W-test.

```
PROC UNIVARIATE DATA=xxxxx NORMAL PLOT;
  VAR yyyy;
  QQPLOT yyyy /NORMAL (MU=EST SIGMA=EST COLOR=RED L=1);
RUN;
```

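### The primary ANOVA gives every subject's rate equal weight whatever the number of sessions behind it, so power is at risk if early dropout or few qualified sessions leave some subjects with very small denominators

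*Protocol*

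**What the plan says.** - **Unit and test.** Protocol 12.4.1 and SAP 4.3.6 form one incidence rate per subject over the 12 outpatient weeks. SAP 4.3.6 then says: "The primary efficacy analysis will be analyzed by ANOVA comparing the mean incidence rate between the three treatment groups".
- **Code.** In SAP Appendix 1 treatment is the only model term ("MODEL param = trt_o"), and none of the alternatives has a WEIGHT statement.
- **Who counts.** ITT is everyone randomized. Per protocol is "ITT participants who completed a qualified exercise session", with further conditions on dosing and eligibility (SAP 4.1), so one qualified session is enough. SAP 2.2 rules out imputation of missing data.
- **Which sessions count.** SAP section 3 limits the primary endpoint to qualified sessions. SAP 2.4 sets conditions on starting glucose, dosing time, type and length of exercise, and heart rate, and keeps only the first qualified session of a day.
- **Expected number.** Footnote i of the schedule (Protocol 2.3) says "subjects will be asked to maintain a weekly exercise average of 2 to 3 sessions weekly of at least 30 minutes". This is a requested average, neither a minimum nor a cap.
- **Sample size.** Protocol 12.2: "With an effect size estimate of 0.262 (variance of means 59, common standard deviation 15), 80% power and an alpha of 0.05", from which "14 subjects per treatment group in the Outpatient Stage is required". SAP 1.3 adds: "Accounting for 15% attrition, a total of 48 subjects will be randomized". Session counts play no part in this calculation.

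**The concern.** A rate from a single session can only be 0% or 100%, and one from two sessions only 0%, 50% or 100%. A rate from 24 to 36 sessions is far more stable. One-way ANOVA treats them alike, so a few subjects with very small denominators can raise the residual SD above the planned 15 and lower the power of the only primary test.

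There are two routes to small denominators: leaving early, and staying but having few sessions that qualify. The sample size treats the 15% attrition as contributing nothing, but the analysis as written keeps any such subject with a computable rate, at full weight. The problem lies within each arm and would exist even if the arms had equal variances.

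**Working it through.** **Inputs from the documents.** Three arms at 1:1:1; 48 randomized, so 16 per arm; 15% attrition, so 0.15 × 16 = 2.4 per arm; SD 15; variance of means 59; overall F-test at 0.05; 2 to 3 sessions × 12 weeks = 24 to 36.

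**Assumptions.** The SD is in percentage points and applies at about 30 sessions. There is at most one event per session, and rates are beta-binomial. The two glucagon arms are equal. The control rate is 35%, with 25 to 40% as the range; the pilot in Protocol 4.2 had 5 of 15, or 33%, with insulin reduction. Leavers' session counts are assumed, and leaving is unrelated to the subject's own rate.

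**1. The plan's own figure.** f² = 59/15² = 59/225 = 0.262. With 14 per arm the noncentrality is 42 × 0.262 = 11.0 on 2 and 39 degrees of freedom, and power is 82.3%. With 13 per arm it is 78.9%. So 14 is correct.

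**2. Variance of one subject's rate.** Arm means of 35, 18.7 and 18.7% have variance (10.87² + 5.43² + 5.43²)/3 = 59. The average of p(1−p) is (0.2275 + 0.1520 + 0.1520)/3 = 0.1772. Setting the total variance at 30 sessions to 0.15² = 0.0225 gives a between-subject part of (0.0225 − 0.1772/30)/(1 − 1/30) = 0.0172. The rest is 0.1600, so V(n) = 0.0172 + 0.1600/n.

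- V(1) = 0.1772, SD 42 points
- V(2) = 0.0972, SD 31 points
- V(24) = 0.0238, SD 15.4 points
- V(36) = 0.0216, SD 14.7 points

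**3. Residual SD with 15% leavers.** If they leave after 1–2 sessions, their mean variance is (0.1772 + 0.0972)/2 = 0.1372. The mixture is 0.85 × 0.0225 + 0.15 × 0.1372 = 0.0397, SD 19.9. If they are spread over 1–30 sessions, their mean variance is 0.0385. The mixture is 0.0249, SD 15.8.

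**4. Power by simulation.** 16 per arm, completers with 24–36 sessions, control 35%. Weights are those of step 6.

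| Leavers' sessions | Residual SD | Unweighted | Weighted |
|---|---|---|---|
| 1–2 | 19.9 | 64% | 81% |
| 1–4 | 18.5 | 70% | 82% |
| 1–8 | 17.3 | 75% | 83% |
| 1–12 | 16.7 | 78% | 83% |
| spread, 1–24 to 1–35 | 15.7–16.0 | 82–84% | 85–86% |

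In the 1–2 row, control rates of 25% and 40% give 72% and 62% unweighted.

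**5. Few qualified sessions.** Let dropout be evenly spread, but let an assumed quarter of subjects qualify in only 10% of their sessions. Unweighted power is 59–70% and weighted 76–80% for control rates of 40% to 25%. At 20% qualifying, the figures are 70–77% and 79–81%.

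**6. Weights.** Since V(n) is proportional to (1+(n−1)ρ)/n, the inverse-variance weight is n/(1+(n−1)ρ). Step 2 implies ρ = 0.0172/0.1772, about 0.10. At 0.10, counts of 1, 2, 24, 30 and 36 get weights 1.0, 1.8, 7.3, 7.7 and 8.0. Completers stay almost equal.

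**7. Type I error.** Unweighted ANOVA: 4.2–4.8% at a common rate of 25% with early leavers. Weighted, ρ = 0.10: 4.7–5.1%, and 4.2–5.8% when the true intraclass correlation is 0.05–0.20 and the common rate 5–25%. Raw session-count weights: 6.4–7.0% under early departure.

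**The case against.** A reader might infer that the trial is underpowered, or that 14 per arm is wrong. The documents support neither. They give no dropout timing, and the plan already discounts leavers entirely. When dropout is spread over the 12 weeks, partial data from later leavers add to the 14 per arm, and unweighted power exceeds 80%. This stands, and it makes the shortfall conditional.

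Three further points stand in part.

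- **Losses before the outpatient phase.** Randomization happens once, at Visit 3. Subjects lost during the CRC phase have no outpatient rate and cannot inflate the variance. If half the leavers go then, unweighted power with 1–2, 1–4 and 1–12 sessions is 68%, 73% and 78%.
- **The non-normality rule.** SAP 4.3.6 moves to non-parametric tests when normality fails. Applying Kruskal-Wallis whenever Shapiro-Wilk rejects gives 70%, 75%, 80% and 83% in the first four rows of the table. That recovers part of the loss. However, the overall test named there is Friedman's, which does not fit parallel arms; Kruskal-Wallis appears only for pairwise comparisons.
- **The target of estimation.** Unweighted means describe the average subject, a defensible choice in a Phase 2 study of preliminary efficacy. Weighting favours those who stay, and anyone who leaves because of hypoglycemia counts less. In a simulation where leaving depended on the subject's own rate, weighting moved arm means by under 1 point, left the arm difference unchanged and kept type I error at 4.5–4.7%.

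**Conclusion.** The structural point holds: equal weights, no minimum session count, and a filter that can leave even completers with few countable sessions. The consequence is a conditional loss of power. Unweighted power is 82–84% with evenly spread dropout. It is about 60–72% if attrition falls mostly in the first one to four sessions, or if an assumed quarter of subjects have very few qualified sessions.

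This rests on the beta-binomial model, on SD 15 holding at about 30 sessions, on control rates of 25–40%, and on assumed departure and qualification patterns. The planned test does not reject too often, so no false-positive concern follows. The change is worth making because weighted power was higher in every pattern examined, and because weights chosen after unblinding would not be credible.

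**What to change.** 1. Define the rate in Protocol 12.4.1 and SAP 4.3.6 as hypoglycemic events divided by qualified sessions. Both now describe sessions divided by events, which is undefined for a subject with no event.
2. In SAP 4.3.6, prespecify weights n/(1+(n−1)ρ), with n the number of qualified sessions and ρ fixed in advance (for example 0.10). Add a WEIGHT statement to the PROC GLM code in Appendix 1.
3. Keep the unweighted ANOVA as a sensitivity analysis.

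A beta-binomial model, or a binomial model with a subject random effect, is an acceptable alternative. Raw session-count weights are not, nor is a quasi-binomial model, which weights in the same way: their type I error is about 5–7%.

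The cost is SAP wording and one line of code. ρ must be chosen before unblinding, and subjects with few sessions, including any who leave because of hypoglycemia, count less. If all subjects lose sessions equally, the gain is only 2 to 4 points of power.
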